Appendix B: SAP checklist.

| Section | Index | Page | Description |
|---------------------------|-------|---------|---|
| 1: Administration | 1a | 1 | Title matches the protocol with SAP as forerunner or subtitle |
| | 1b | 1 | Trial registration number |
| | 2 | 1 | SAP version number with dates |
| | 3 | 1 | Reference to version of protocol being used |
| | 4a | 1 | SAP revision history |
| | 4b | NA | Justification for each revision |
| | 4c | NA | Timing of SAP revisions in relation to interim analyses |
| | 5 | 1 | Names, affiliations and roles of SAP contributors |
| | 6a | 1 | Person writing SAP |
| | 6b | 1 | Senior statistician responsibility |
| | 6c | 1 | Chief investigator/Clinical lead |
| 2: Introduction | 7 | 5 | Synopsis of trial background and rationale |
| | 8 | 5 | Description of specific objectives or hypothesis |
| 3: Study Methods | 9 | 7 | Brief description of trial design |
| | 10 | 10 | Randomisation details |
| | 11 | 10 | Sample size calcs |
| | 12 | 12 | Superiority/equiv/non-inferiority |
| | 13a | 12 | Info regarding interim analyses |
| | 13b | NA | Adjustment to significance |
| | 13c | NA | Stopping rules |
| | 14 | 12 | Timing of final analysis |
| | 15 | 6 | Time points at which outcomes are measured |
| 4: Statistical principals | 16 | 12 | Level of statistical significance |
| | 17 | 12 | Rationale for multiplicity adjustments and T1 error control |
| | 18 | 12 | Confidence intervals to be reported. |
| | 19a | 6 | Definition of adherence |
| | 19b | 6 | Description of how adherence will be presented |
| | 19c | 6, 8, 9 | Definition of protocol deviations |

| | | | |
|---------------------|-----|--------|--|
| 5: Trial population | 19d | 6 | Description of which deviations will be summarized |
| | 20 | 11 | Definition of analysis populations |
| | 21 | 15 | Reporting of screening data to describe representativeness of trial sample |
| | 22 | 8,9 | Summary of eligibility criteria |
| | 23 | 15 | Information to be included in CONSORT flow chart |
| | 24a | 15 | Level of withdrawal, from intervention and/or follow-up |
| | 24b | 15 | Timing of withdrawals |
| | 24c | 15 | Reasons and details how withdrawals will be presented. |
| | 25a | 15 | List of baseline characteristics to be summarized |
| | 25b | 15 | Details of how baseline characteristics will be summarized |
| 6: Analysis | 26 | 6 | List of primary and secondary outcomes |
| | 26a | 12 | Outcome timings and order of importance |
| | 26b | 10, 11 | Specific measurement and units |
| | 26c | 14 | Calculation or transformation used to derive the outcome |
| | 27a | 14 | Analysis method to estimate treatment effects |
| | 27b | 12 | Covariates adjusted for |
| | 27c | 14 | Methods to check assumptions |
| | 27d | 14 | Details of alternative methods if distributional assumptions do not hold |
| | 27e | 13 | Planned sensitivity analyses |
| | 27f | 14 | Planned subgroup analyses and definitions of subgroups |
| | 28 | 11, 12 | Assumptions methods for dealing with missing data. |

OMIT STUDY – CODE FOR IMPUTATION (R) 18-12-2024

```
#####
```

```
## Data construction
```

```
#####
```

```
{
```

```
## Imputation data set
```

```
imp.data
```

```
## Reformat adherence so that 0 = worst adherence.
```

```
imp.data$adher.w2 <- 5 - as.numeric(imp.data$adher.w2)
```

```
imp.data$adher.w4 <- 5 - as.numeric(imp.data$adher.w4)
```

```
imp.data$adher.w8 <- 5 - as.numeric(imp.data$adher.w8)
```

```
## Calculate mean adherence
```

```
imp.data$adherence <- (as.numeric(imp.data$adher.w2) + as.numeric(imp.data$adher.w4) + 2*as.numeric(imp.data$adher.w8))/4
```

```
## Assume control is group 'C'
```

```
imp.data$treat <- relevel(imp.data$treat, ref='C')
```

```
## Construct log data to present analyses as percentage change.
```

```
for (var. in var.list[var.list %in% data.list$log.list]) {
```

```
for (visit. in c('w0', 'w8')) {  
  
  imp.data[,paste(var., visit., sep='.')] <- log(imp.data[,paste(var., visit., sep='.')])  
  
}; rm(visit.)  
  
}; rm(var.)
```

Variable lists

```
w0.list <- names(imp.data)[grepl('w0', names(imp.data))]
```

```
sum(!w0.list %in% names(imp.data)) # 0
```

```
w0.list <- w0.list[order(colSums(is.na(imp.data[,w0.list])))]; w0.list
```

```
w8.list <- names(imp.data)[grepl('w8', names(imp.data)) & !grepl('adher', names(imp.data))]
```

```
sum(!w8.list %in% names(imp.data)) # 0
```

```
w8.list <- w8.list[order(colSums(is.na(imp.data[,w8.list])))); w8.list
```

```
calculated.list <- c("adherence", "glucose.auc.w0", "insulin.auc.w0", "glucose.auc.w8", "insulin.auc.w8")
```

```
w0.list <- w0.list[!w0.list %in% calculated.list]
```

```
w8.list <- w8.list[!w8.list %in% calculated.list]
```

```
adher.list <- c('drop.out', 'week.drop', 'adher.w2', 'adher.w4', 'adher.w8')
```

```
sum(!adher.list %in% names(imp.data)) # 0
```

```
aux.list <- c("id", "treat", "sex");
```

```
sum(!aux.list %in% names(imp.data)) # 0
```

```
table(table(c(w0.list, w8.list, aux.list, adher.list, calculated.list))) # all 1s
```

```
sum(!names(imp.data) %in% c(w0.list, w8.list, aux.list, adher.list, calculated.list)) # 0
```

```
## List of meal data for formula construction
```

```
meal.list <- c(
```

```
"glucose.auc.break.w0", "glucose.auc.lunch.w0", "glucose.auc.dinner.w0"
```

```
, "insulin.auc.break.w0", "insulin.auc.lunch.w0", "insulin.auc.dinner.w0"
```

```
, "glucose.auc.break.w8", "glucose.auc.lunch.w8", "glucose.auc.dinner.w8"
```

```
, "insulin.auc.break.w8", "insulin.auc.lunch.w8", "insulin.auc.dinner.w8"
```

```
)  
  
sum(!meal.list %in% names(imp.data)) # 0  
  
}
```

```
#####
```

```
## Multiple Imputation
```

```
#####
```

```
## MI
```

```
set.seed(1234)
```

```
M. <- 100; N.iter <- 100
```

```
options(warn=0)
```

```
time. <- Sys.time()
```

```
for (MNAR.type in 0:1) {
```

```
## Code assumes control group = 'C'
```

```
library(mice)
```

```
# Set up data assumptions dropout
```

```
{
```

```
temp.data <- imp.data[, c(w0.list, w8.list, calculated.list, aux.list, adher.list)]
```

```
colSums(is.na(temp.data))
```

```
## MAR: impute unknown drop out reason.
```

```
if (MNAR.type == 0) {
```

```
  temp.data$drop.out[temp.data$drop.out == 'Unknown'] <- NA
```

```
  sum(length(unique(temp.data$drop.out)) != 3) # 0
```

```
}
```

```
## MNAR: Do not impute unknown drop.out, set at best-worst case: A & B due to diet vs C not diet
```

```
if (MNAR.type == 1) {
```

```
  temp.data$drop.out[temp.data$treat == 'C' & temp.data$drop.out == 'Unknown'] <- 'Not diet'
```

```
  temp.data$drop.out[temp.data$treat %in% c('A', 'B') & temp.data$drop.out == 'Unknown'] <- 'Diet'
```

```
  sum(length(unique(temp.data$drop.out)) != 3) # 0
```

```
}
```

```
temp.data$drop.out <- temp.data$drop.out[drop=T]
```

```
if (nlevels(temp.data$drop.out) != 2) cat('Error wrong number of drop options.\n')
```

```

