| Treatment 
 - eCR (30% calorie restriction, 8am – 4pm); - dCR (30% calorie restriction, 12pm – 8pm); - CR (30% calorie restriction, 8am-8pm); Control group | |
| ESTIMAND | ANALYSIS |
| Target population 
 - Men and women with obesity and elevated fasting blood glucose | Analysis set 
 - All randomized - Initiated diet |
| Variable 
 - Glucose AUC over 3 meals (breakfast, lunch, dinner). | Outcome measure 
 - Blood glucose AUC - Measured at 0,30,60,120 post-meal - Averaged over three meals |
| Handling of inter-current events 
 1. Death (while on treatment strategy, or “while alive”) 2. Discontinuation: other reason (while on treatment strategy) 3. Discontinuation: dislike of diet (treatment policy strategy) 4. Lost-to-follow-up no reason provided (treatment policy strategy) | Handling of missing data 
 1. Death believed not to be relevant for this study, included for completeness. 2. All individuals discontinuing early will (i) be invited to attend the week 6 assessment for fasting bloods and body weight only, (ii) asked whether the reason for discontinuation is due to allocated diet. 3. Missing-at-random will be assumed for individuals who do not specify whether discontinuation was due to diet, or when the reason was not due to the diet. 4. For individuals who discontinued due to the diet a missing-not-at-random assumption will be made, assuming zero adherence after discontinuation, and conditional on adherence missing-at-random assumed to impute week 8 outcomes. |

| | |
|---|--|
| | 5. Imputation is by treatment group with individuals imputed in the groups they were allocated to. |
| Population level summary measure 
 - Mean between group differences in baseline adjusted log-transformed (within-individual) mean post-meal glucose AUC, of the time-restricted groups versus the control (non time-restricted) group. | Analysis approach 
 - Group differences of log transformed mean post-prandial AUC will be estimated using a single linear regression with a treatment (three levels) and baseline log transformed mean post-prandial glucose AUC and stratification factors (sex and fasting plasma glucose). |

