Hypothesis testing framework: All analyses are to test for superiority of eCR and dCR over CR.

Analyses: No interim analyses are planned. The analysis of the primary outcome will be conducted after the final subject has completed their 8 week assessment and the blood samples assessed for glucose concentrations.

Error Control: There are two primary comparisons, eCR vs CR and dCR vs CR with a common control and thereby use a Dunnett multi-test adjustment that controls the familywise error rate at 0.05 (two-sided) when each pairwise test uses an alpha of 0.027 (two-sided).

There are four secondary efficacy outcomes that will be tested to support a confirmatory finding: (i) PP insulin AUC, (ii) fasting insulin, (iii) fasting glucose, and (iv) HbA1c. An ordered testing procedure with per comparison (eCR vs CR and dCR vs CR) will be applied testing these four secondary outcomes in the order listed here, testing each subsequent outcome only if the previous outcome (and primary outcome) rejected the null. This procedure is applied separately for each comparison: eCR vs CR and dCR vs CR. The same pairwise alpha level, 0.027 (two sided), as the primary outcome will be applied to ensure that the familywise error rate is controlled at 0.05 (two-sided).

Standard multiplicity unadjusted 95% confidence intervals will be reported for all comparisons.

Covariate adjustment: All comparisons of treatment effect will include adjustment for...

1. The outcome variable's baseline assessment if appropriate,
2. Stratification factors (sex and baseline fasting plasma glucose as a continuous variable)

Sensitivity Analyses: A best-worst case sensitivity analysis will be performed for the analysis of the primary outcome and secondary efficacy outcomes.

- For all individuals missing the week 8 assessment in the CR (control) group the outcome will be imputed assuming missing-at-random. In other words, as if each individual's mean adherence was continued, or the cohort's mean adherence if no adherence data is available for an individual.
- For individuals missing the week 8 assessment in the eCR and dCR groups their outcome, a missing-not-at-random assumption will be applied by assuming zero adherence and outcomes imputed thereafter, i.e., assuming missing-at-random conditional on zero subsequent adherence.
- These assumptions will be made irrespective of the stated reason for diet discontinuation.

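### The best-worst sensitivity code changes only drop-outs with an unknown reason, while the SAP text applies the rule to everyone missing week 8, so the reported analysis may be weaker than the one described

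*SAP*

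**What the plan says.** **Primary analysis** (SAP, Estimand Considerations table, handling of missing data). Two rules depend on the reason for stopping, and neither depends on arm. First, with the closing word (diet) cut off here: "Missing-at-random will be assumed for individuals who do not specify whether discontinuation was due to diet, or when the reason was not due to the". Second: "For individuals who discontinued due to the diet a missing-not-at-random assumption will be made, assuming zero adherence after discontinuation".

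**Best-worst analysis, text** (SAP, Sensitivity Analyses). The rule depends on arm and not on reason. For control: "For all individuals missing the week 8 assessment in the CR (control) group the outcome will be imputed assuming missing-at-random". For eCR and dCR: "a missing-not-at-random assumption will be applied by assuming zero adherence and outcomes imputed thereafter". The scope is explicit: "These assumptions will be made irrespective of the stated reason for diet discontinuation". It covers the primary outcome and the four secondary efficacy outcomes, and Table A2 is its shell.

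**Best-worst analysis, code** (SAP, Code for imputation, run with `MNAR.type` equal to 1). The comment has a narrower scope: "MNAR: Do not impute unknown drop.out, set at best-worst case: A & B due to diet vs C not diet". The line for the time-restricted arms is "temp.data$drop.out[temp.data$treat %in% c('A', 'B') & temp.data$drop.out == 'Unknown'] <- 'Diet". The line for C has the same condition and sets unknown reasons to not diet. In the primary run (`MNAR.type` equal to 0) unknown reasons are instead set to missing: "temp.data$drop.out[temp.data$drop.out == 'Unknown'] <- NA".

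**The concern.** The text calls for a stress test that overrides what participants said about why they stopped. The code overrides nothing that was said; it only fills in what was not said. The two agree only for drop-outs whose reason is unknown, or whose stated reason happens to match the arm's rule.

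This is the only planned analysis that departs further from MAR than the primary analysis does. The other sensitivity analysis, complete case, does not test such a departure. The code labels the output as the worst-case imputation and Table A2 is titled as the best-worst case, so a reader would take it for the bound described in the text. If it moves little because few reasons were unknown, the result would look robust without the stated test having been done.

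**Working it through.** **1. Where the code could apply the rule.** After the recode, three places matter.
- The loop that sets adherence to zero after the drop-out week runs only over participants coded as diet, in any arm and in both runs.
- The imputation formulas for adherence also treat only the diet code as non-adherent.
- `MNAR.type` is otherwise used only to store, select and label results and to trigger the complete-case rows.

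Both runs start from the same data set. Nothing later overrides a stated reason.

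**2. Text against code, by arm and recorded reason** (A and B time-restricted, C control).

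| Arm | Recorded reason | SAP text | Code | Agree |
|---|---|---|---|---|
| A | Diet | zero adherence | zero adherence | yes |
| A | Not diet | zero adherence | MAR | **no** |
| A | Unknown | zero adherence | zero adherence | yes |
| B | Diet | zero adherence | zero adherence | yes |
| B | Not diet | zero adherence | MAR | **no** |
| B | Unknown | zero adherence | zero adherence | yes |
| C | Diet | MAR | zero adherence | **no** |
| C | Not diet | MAR | MAR | yes |
| C | Unknown | MAR | MAR | yes |

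Three of nine cells disagree. They are exactly those in which a stated reason had to be overridden. A participant with no week 8 data and a blank reason is not recoded either; the reason is imputed in both runs.

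**3. No unknown reasons.** The recode then touches nobody, and the data entering `mice` are the same in both runs. The seed is set once, before the loop over runs, so the draws differ. The results differ only by Monte Carlo error with 100 imputations.

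**4. Standard error of a contrast.** Inputs from Pre-planned Sample size: 38 per group, SD 0.152 on the log scale, pre-post correlation 0.85, drop-out below 10%, difference 0.06, alpha 0.027 two-sided.
- Residual SD = 0.152 × √(1 − 0.85²) = 0.0801.
- Completers per arm = 38 × 0.9 = 34.2.
- SE = 0.0801 × √(2/34.2) = 0.0194.
- Check against the plan: power at these values is 0.8125, so the stated figure of more than 80% is reproduced.

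**5. Illustrative size.** The SAP gives neither the mix of reasons nor the cost of non-adherence. Assume the same mix in each arm and that zero adherence raises log AUC by 0.06 per person relative to MAR. The shift against a time-restricted arm is then (zero-adherence drop-outs in that arm minus those in control) / 38 × 0.06.

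| Drop-outs per arm (diet / not diet / unknown) | Shift under text | Shift under code | Gap |
|---|---|---|---|
| 3 (1/1/1) | 3/38 × 0.06 = 0.0047 | 1/38 × 0.06 = 0.0016 | 0.0032 |
| 4 (1/2/1) | 4/38 × 0.06 = 0.0063 | 1/38 × 0.06 = 0.0016 | 0.0047 |
| 4 (0/2/2) | 0.0063 | 2/38 × 0.06 = 0.0032 | 0.0032 |
| 4 (2/2/0) | 0.0063 | 0 | 0.0063 |
| 4 (0/0/4) | 0.0063 | 0.0063 | 0 |

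For the first two rows the gap is 0.0032/0.0194 = 0.16 to 0.0047/0.0194 = 0.24 of a standard error. Even the full rule in the text moves the contrast by only 0.0063/0.0194 = 0.33 of one.

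**The case against.** The mismatch itself cannot be argued away, but four points limit what follows from it.

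- **Reach.** The primary estimate, the 0.027 pairwise tests and the ordered secondary tests all come from the other run. Table A2 has no p-value columns. This stands: no confirmatory decision depends on this code.
- **Size.** The illustration leans upward. Four of 38 is 10.5%, above the planned limit of 10%; three of 38 is 7.9%. A cost of 0.06 per person equals the whole difference the trial is powered for, and nothing in the SAP ties that loss to non-adherence. The code also zeroes only adherence after the drop-out week, and mean adherence is (w2 + w4 + 2 × w8)/4, so someone leaving between weeks 4 and 8 keeps the first half of the weight. All of this stands.
- **How much weaker.** A reader might infer that the coded analysis is far weaker than the stated one. The SAP does not support that as a fact. Text and code agree if every reason is unknown, or if stated non-diet reasons occur only in C and stated diet reasons only in A and B. Against that, participants who stop are to be asked whether the diet was the reason. The code's check in the primary run, made after unknown reasons are blanked, also expects both stated reasons to be present. Some disagreement is therefore likely, but its extent is open.
- **Direction.** A reader might also infer that keeping control diet drop-outs at zero adherence turns the analysis into the opposite of a worst case. It does not. That is the primary analysis's own assumption, left as it was. Relative to the primary analysis, the recode acts only against the time-restricted arms. It is a partial worst case, not a reversed one.

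**Conclusion.** The text and the code specify different analyses under one name. As coded, the best-worst analysis varies only unknown reasons. It may be weaker than the bound the SAP describes, depending on the mix of reasons, and it collapses to the primary analysis, up to Monte Carlo error, when no reason is unknown. The contradiction follows from the two rules alone and needs no assumed number.

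Its size does rest on assumptions. With one unknown reason among 3 to 4 drop-outs per arm, the same mix in each arm and a cost of 0.06 log units, the gap is about 0.003 to 0.005 log units, or roughly a sixth to a quarter of the contrast standard error. Across the four-drop-out mixes shown it runs from 0 to 0.0063. This should be fixed because a prespecified robustness analysis would otherwise be reported without having been performed. It is not a threat to the primary result.

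**What to change.** Choose one of two routes before the analysis is run.

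**Make the code follow the text.** In the run with `MNAR.type` equal to 1:
1. Define the indicator for missing week 8 before the recode. The code builds the matching condition only in the next block, from week 8 variables other than fasting glucose.
2. Remove the condition on unknown reasons. Among participants missing week 8, set `drop.out` to diet for all in A and B and to not diet for all in C, whatever is recorded, including blanks.
3. Make sure `week.drop` is filled for everyone recoded to diet, by a stated convention. A missing value would stop the zero-adherence loop at its first comparison.
4. Then run that loop and the imputation as now.

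**Or make the text follow the code.** If only unknown reasons are meant to vary, amend Sensitivity Analyses to say so, delete the sentence on scope, and rename the analysis there and in Table A2 so that it is no longer called best-worst.

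The first route costs a few lines of code, a convention for missing drop-out weeks and a rerun of one imputation; the sensitivity result may look less favourable. The second costs only wording, but leaves the trial without the stronger stress test. Neither changes the primary analysis or the sample size.

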## Set individuals who did not discontinue to 'Not diet' drop out at week 8 (ie so data is not imputed)
```

```
cond. <- rowSums(!is.na(temp.data[,w8.list[w8.list != 'fasting.glucose.w8']])) > 0
```

```
temp.data$drop.out[is.na(temp.data$drop.out) & cond.] <- 'Not diet'
```

```
temp.data$week.drop[is.na(temp.data$week.drop) & cond.] <- 8; rm(cond.)
```

```
## Set adherence to "Strongly Disagree" (ie 0) when due to diet and after drop-out week
```

```
for (id. in temp.data$id[temp.data$drop.out == 'Diet' & !is.na(temp.data$drop.out)]) {
```

```
week. <- temp.data$week.drop[temp.data$id == id.]

if (week. < 2) temp.data$adher.w2[temp.data$id == id.] <- 0

if (week. < 4) temp.data$adher.w4[temp.data$id == id.] <- 0

if (week. < 8) temp.data$adher.w8[temp.data$id == id.] <- 0

rm(week.)

}; rm(id.)

## Calculate mean adherence over the eight weeks.

temp.data$adherence <- ((temp.data$adher.w2) + (temp.data$adher.w4) + 2*(temp.data$adher.w8))/4

}
```

```

# Set up imputation functions

{

fm.list <- NULL

for (var. in w0.list) { # [!sub('.w0', '', w0.list) %in% data.list$log.list]

  if (!var. %in% meal.list) {

    fm. <- paste(var., "~ sex + ", paste(c(w0.list[!w0.list %in% c(var., meal.list)], "glucose.auc.w0", "insulin.auc.w0"), collapse=' + '))

    fm.list <- c(fm.list, as.formula(fm.)); rm(fm.)

  } else {

    fm. <- paste(var., "~ sex + ", paste(c(w0.list[!w0.list %in% (var.)]), collapse=' + '))

    fm.list <- c(fm.list, as.formula(fm.)); rm(fm.)

  }
}

```

```

}; rm(var.)

for (var. in w8.list) {

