- current smokers of cigarettes/marijuana/e-cigarettes/vaporisers
- anyone unable to comprehend the study protocol or provide informed consent (i.e. due to English language or cognitive difficulties)
- do not own, or are not comfortable using, a smartphone and applications

Individuals with dietary restrictions or practices, including vegans and those with gluten or nut allergies will be excluded. Less restrictive dietary practices including vegetarians and those with lactose intolerance or specific dietary dislikes will be accommodated.

Pre-planned Sample size

An expected group difference is 0.46 mmol/L at 2-hrs after a glucose tolerance test (1). Our past data, DIRECT study (2) showed a mean glucose concentration of 7 mmol/L at two hours post meal. We note that $0.46/7.0$ is a 6.5% reduction. T4DM powered for a 0.6 mmol/L between group difference, which is approximately 6% change from baseline in a population including individuals with diabetes (3). We thereby assumed the MCID to be a 6% reduction from baseline in mean post meal AUC and use log (AUC) to estimate of the percentage difference between groups (4).

Using data from the DIRECT study (2), the SD of the log (meal test AUC) is expected to be 0.152 and pre-post AUC correlations were 0.87 at breakfast and 0.92 at dinner.

With $N=114$ (38 per group, randomized 1:1:1), a within-group SD of 0.152, pre-post correlation of at least 0.85 and a drop-out rate less than 10%, there is >80% to detect a difference of 0.06 in log-transformed AUC in a baseline adjusted ANCOVA ($\alpha = 0.027$ two-sided) (5).

Sample size adaption

None

Randomization details

Stratified random length blocked randomisation by sex (male or female) and fasting plasma glucose (≤ 6.0 vs >6.0 mmol/L)

STATISTICAL CONSIDERATIONS

Estimand Considerations

| | |
|--|---|
| Study objective 
 - To establish whether early or delayed time-restricted eating plus calorie restriction (eCR, dCR), improve markers of type 2 diabetes, compared with calorie restriction (CR) alone | |
| Estimand 
 - The difference in percentage change from baseline in the mean 2-hour post-meal glucose AUC levels after eight weeks of time restricted versus non-time restricted dieting, in obese men and women | |

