A secondary, complete-case sensitivity analysis will be performed for the analysis of the primary outcome and secondary efficacy outcomes in this analysis individuals with both baseline and week 8 assessments will only be included for each analysis.

As additional analysis will explore the treatment effects within subjects who were adherent to the protocol using data collected with the MyCircadianClock app plus the dietary checklists. This analysis will be reported in a secondary mechanistic publication of this study.

STATISTICAL METHODS

Primary Outcome

The primary analysis of the primary outcome is a covariate adjusted linear regression of the differences in PP glucose log AUC at 8 weeks from baseline. Covariates included will be treatment (three groups), baseline glucose log AUC, sex and fasting plasma blood glucose (as a continuous linear variable). Visual inspection of the residual distribution will be used to determine if assumptions of normality and the absence of a variance-mean association appear to be violated. If assumptions appear violated a generalized linear models will be considered with differing link functions will be considered and presented as sensitivity analyses. Given the limited sample size, no subgroup analyses are planned.

This analysis will be performed in all randomized individuals with individuals using multiple imputation using chained equations within treatment groups and combined using Rubin's rules. The variables used in the multiple imputation are age and sex; baseline and week 8 assessments of weight, PP glucose and insulin AUC (per meal), fasting glucose, fasting insulin and HbA1c; and the self-reported adherence over the 8 weeks and reason for discontinuation (related/unrelated to diet) if applicable. All concentrations will be imputed on the log scale, with the 3-meal mean of PP glucose and insulin AUC being calculated on the original scale after a back-transformation. Compliance will be imputed as per the intercurrent event strategies and the average compliance calculated over each period. Imputation will use multiple chained equations (*mice* R package), details of which are attached separately (file: *OMIT – Imputation code 2024-12-18.r*).

Secondary Efficacy Outcomes

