## Construct calculated methods
```

```
{
```

```
method.[names(method.) == 'glucose.auc.w0'] <- gsub(
```

```
'\n', '',
```

```
"~ |("
```

```
log((
```

```
exp(glucose.auc.break.w0)
```

```
+ exp(glucose.auc.lunch.w0)
```

```
+ exp(glucose.auc.dinner.w0)
```

)/3)

)"

)

```
method.[names(method.) == 'insulin.auc.w0'] <- gsub(
```

```
"\n", "
```

```
"~ |("
```

```
log((
```

```
exp(insulin.auc.break.w0)
```

```
+ exp(insulin.auc.lunch.w0)
```

```
+ exp(insulin.auc.dinner.w0)
```

)/3)

```
)"
```

```
)
```

```
method.[names(method.) == 'glucose.auc.w8'] <- gsub(
```

```
"\n", "
```

```
"~ | (
```

```
log((
```

```
exp(glucose.auc.break.w8)
```

```
+ exp(glucose.auc.lunch.w8)
```

```
+ exp(glucose.auc.dinner.w8)
```

```
)/3)
```

```
)"
```

```

)

method.[names(method.) == 'insulin.auc.w8'] <- gsub(

'\n', ", ",

"~ |("

log((

exp(insulin.auc.break.w8)

+ exp(insulin.auc.lunch.w8)

+ exp(insulin.auc.dinner.w8)

)/3)

)"

)

```

```

method.[names(method.) == 'adherence'] <- gsub(

  '\n', "",

  "~ |("

  ((

    as.numeric(adher.w2)

    + as.numeric(adher.w4)

    + 2*as.numeric(adher.w8)

  )/4)

  )"

)

}

```

```
}
```

```
for (treat. in c('A', 'B', 'C')) {
```

```
  mice.fit2 <- mice(
```

```
    data=temp.data[temp.data$treat == treat.,]
```

```
    , m=M., maxit=N.iter
```

```
    , blocks=var.list
```

```
    , visitSequent=var.list
```

```
    , formulas=fm.list
```

```
    , method=method.
```

```
    , print=F
```

```
)
```

```
mice.fit2$loggedEvents
```

```
if (treat. == 'A') mice.fit.A <- mice.fit2
```

```
if (treat. == "B") mice.fit.B <- mice.fit2
```

```
if (treat. == "C") mice.fit.C <- mice.fit2
```

```
rm(mice.fit2)
```

```
}; rm(treat.)
```

```
rm(mice.fit, method., fm.list, var.list)
```

```

if (MNAR.type == 0) mice.full.fit0 <- rbind(rbind(mice.fit.A, mice.fit.B), mice.fit.C)

if (MNAR.type == 1) mice.full.fit1 <- rbind(rbind(mice.fit.A, mice.fit.B), mice.fit.C)

rm(mice.fit.A, mice.fit.B, mice.fit.C)

}; rm(MNAR.type)

rm(M., N.iter, temp.data, adher.list, aux.list, meal.list, calculated.list, w0.list, w8.list)

ls()

#####

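### Missing baseline values are imputed without the week-8 values, so if any baselines are missing the primary comparison gets a standard error that is too large

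*SAP*

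**What the plan says.** The SAP's Primary Outcome section plans multiple imputation by chained equations within treatment group, pooled by Rubin's rules. It names the inputs: "The variables used in the multiple imputation are age and sex; baseline and week 8 assessments of weight", followed by the per-meal glucose and insulin AUCs, fasting glucose, fasting insulin, HbA1c, adherence and reason for discontinuation. The primary model adjusts for baseline glucose log AUC.

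The attached R code, under its comment on setting up imputation functions, builds one formula per variable:

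- **Baseline meal AUC:** sex plus "paste(c(w0.list[!w0.list %in% (var.)]), collapse", that is, every other baseline variable.
- **Baseline non-meal value:** sex, the other non-meal baseline variables, and the baseline mean glucose and insulin AUCs.
- **Any week-8 value:** its own baseline counterpart, sex, adherence, baseline fasting glucose and other week-8 variables. Non-meal values also get the mean AUCs at both visits.

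No week-8 variable enters either kind of baseline formula. The formulas are run arm by arm, with "data=temp.data[temp.data$treat == treat".

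The sample size section relies on "With $N=114$ (38 per group, randomized 1:1:1), a within-group SD of 0.152" and a "pre-post correlation of at least 0.85 and a drop-out rate less than 10" per cent, giving more than 80% power "to detect a difference of 0.06 in log-transformed AUC in a baseline adjusted ANCOVA ($\alpha = 0.027$ two-sided".

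**The concern.** When a covariate of the outcome model is imputed, the outcome belongs in the imputation model. Otherwise the imputed covariate is related to the outcome only as far as the other predictors carry that relation. Here the pre-post link is used in one direction only: week 8 is imputed from baseline, but baseline is not imputed from week 8.

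This matters because the trial's precision rests on that link. With a pre-post correlation of 0.85, baseline adjustment leaves 27.75% of the variance. A participant whose baseline is drawn without sight of their own week-8 value gets little of that benefit. The draw also adds between-imputation variance that Rubin's rules count in full.

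The code provides for missing baselines. It defines derived imputation methods for the baseline mean AUCs, and its complete-case analysis removes missing values when averaging baseline. How many will be missing is not stated.

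**Working it through.** **1. The plan's own figure.** Inputs from the sample size section: SD 0.152, correlation 0.85, 38 per arm less 10% = 34.2, difference 0.06, two-sided alpha 0.027.

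- Residual SD = 0.152 × √(1 − 0.85²) = 0.0801.
- SE of the difference = 0.0801 × √(2/34.2) = 0.0194.
- Power = Φ(0.06/0.0194 − 2.21) ≈ 0.81.

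The claim of more than 80% reproduces (0.8125).

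**2. Residual variance of an affected participant.** Work in units of the total variance. Let R² be the share of baseline variance explained by the other baseline variables (an assumption, not in the SAP). Baseline is drawn without week 8, so its covariance with week 8 is r·R². The residual variance about a slope of r is 1 + r² − 2r²R². For everyone else it is 1 − 0.85² = 0.2775.

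| R² | Residual variance | Ratio to 0.2775 |
|---|---|---|
| 0.30 | 1.29 | 4.6 |
| 0.36 (correlation 0.6) | 1.20 | 4.3 |
| 0.60 | 0.86 | 3.1 |
| 0.81 (correlation 0.9) | 0.55 | 2.0 |

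The code's response is change from baseline. With baseline also a covariate, this gives the same treatment estimate and SE as week 8 as the response, so the argument carries over.

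**3. Simulated power, whole baseline missing.** Assumptions: three arms of 34 with week 8 observed; baseline missing completely at random; normal-model imputation within arm; 20 imputations; Rubin's rules with small-sample degrees of freedom; 4,000 trials per cell (Monte Carlo error about 0.7 point). With nothing missing, power is 0.79-0.81.

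| Missing per arm | Correlation with other baseline data | As coded | Week 8 added |
|---|---|---|---|
| 1 | 0 | 0.71 | 0.78 |
| 2 | 0 | 0.63 | 0.77 |
| 3 | 0 | 0.56 | 0.76 |
| 1 | 0.6 | 0.75 | 0.80 |
| 2 | 0.6 | 0.69 | 0.78 |
| 3 | 0.6 | 0.62 | 0.76 |
| 1 | 0.9 | 0.79 | 0.80 |
| 2 | 0.9 | 0.77 | 0.79 |
| 3 | 0.9 | 0.74 | 0.77 |

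A separate simulation at correlation 0.6 gave 0.73, 0.67 and 0.63 as coded, against 0.79, 0.76 and 0.76. At correlation 0.9 it gave a loss of about 3 to 5 points.

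**4. Standard error, slope and bias** (3 per arm, correlation 0.6).

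- The baseline slope is 0.79 as coded and 0.85 with week 8 added.
- The mean pooled SE is 0.0236 against 0.0202, and 0.0236/0.0202 = 1.17.
- The true sampling SE as coded is 0.0214 (0.0207 in the separate simulation), so the pooled SE overstates it by 10 to 14%.
- Bias in the treatment effect is below 0.001.
- Under the null, the rejection rate is 0.008 (0.013 in a repeat run) against a nominal 0.027.
- Complete-case power is 0.75, so here the imputed analysis (0.62) does worse than leaving these people out.

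**5. One of three baseline meals missing.** For 2 or 4 of 34 per arm and inter-meal correlations of 0.6 or 0.8, power is 0.77-0.79 as coded and 0.79-0.80 with week 8 added. The loss is about 0 to 3 points (1,500 trials per cell, error about 1 point).

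**The case against.** The strongest objection is that the trigger is not shown. The fault needs someone with an observed week 8 and a missing baseline, and the SAP gives no rate for that. Its missing-data plan concerns discontinuation, its power calculation allows only for drop-out, and the sorting of baseline variables by number missing is done in the same way for week 8. This stands: the consequence is conditional, and it is nil if baselines are complete.

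The size also depends on an R² that the SAP does not give. The AUC includes a time-0 sample and fasting glucose is a predictor, so a high R² is plausible, and then only a few points are lost. This stands too, which is why a range is given. Repeating the check with predictive mean matching kept the direction.

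Four stronger readings are tempting and not supported:

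- A reader might infer that the pre-post relation is lost, or that the treatment effect is biased. The relation is attenuated, the estimate is unbiased, and the error is on the conservative side.
- A reader might infer that code and text flatly contradict each other. The text lists variables for the imputation as a whole and does not say that every equation uses all of them.
- A reader might infer a similar loss for the four secondary outcomes. They share the formulas, but the SAP gives no SD or pre-post correlation for them, so no size can be computed.
- A reader might infer that age is left out altogether. The construction of the data set is not shown, and the baseline list takes any variable with w0 in its name, so age may be in it. Its absence is established only for the week-8 formulas.

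The complete-case sensitivity analysis would expose an inflated standard error, but it does not repair the primary analysis.

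**Conclusion.** The point holds as a conditional fault in the code. Missing baselines are drawn without the outcome of the model in which baseline is a covariate. If any participant with an observed week 8 lacks a baseline, the primary comparison loses precision and its confidence intervals and p-values are too conservative.

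With 1 to 3 whole baselines missing of 34 per arm and a correlation of 0.6, the loss in power for glucose AUC runs from about 5 to 14 points. It is smaller under the milder assumptions above, and about 7 to 21 points if the other baseline data carry no information. All these figures assume baselines missing at random with respect to outcome, the SAP's SD of 0.152 and a correlation of 0.85.

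**What to change.** In each baseline formula, add the matching week-8 variable where one exists. For meal AUCs, also add the other week-8 meals of the same analyte if the model remains estimable. In the non-meal baseline formulas, add `glucose.auc.w8` and `insulin.auc.w8`. A blanket swap of w0 for w8 in the variable name would fail for any baseline variable with no week-8 counterpart, so the code should test for one first.

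Add age to the week-8 formulas, and to the baseline formulas if it is not already in `w0.list`. Then rerun, and report how many baseline values were imputed per arm. If the outcome is left out on purpose, say why.

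The cost is a few lines of code and more predictors in small within-arm models. If `w0.list` holds just the ten baseline measures that the text names (six meal AUCs, weight, fasting glucose, fasting insulin, HbA1c), a meal formula now has sex + 9 = 10 predictors. It would have 11 with its own week-8 value and 13 with the other two week-8 meals, before age, for at most 38 people per arm. No new data are needed, unless age has to be brought into the imputation data set.
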